5.3. Selection and Timing of Dose for Each Subject

5.3.1. General Instructions for Dosing

Lesinurad 200 mg once daily is the currently approved dose by the FDA and EMA and is under evaluation in this study. Only doses of XOI that are approved by the local product labels are permitted in this study.

All doses of IP should be taken daily, in the morning with food and 1 cup (8 oz; 240 mL) of water. Subjects should be instructed to drink 2 liters (68 oz) of liquid a day. For example, another 3 cups (24 oz; 720 mL) of liquid during the 3 to 4 hours after taking the IP should be encouraged, and then the subject should remain well hydrated (an additional 4 cups [32 oz; 960 mL] of liquid) throughout the day.

IP must be taken at the same time as the morning dose of XOI. Missed doses of IP should not be taken later in the day (eg, in the afternoon or evening) or made up on the following day.

Subject should take gout flare prophylaxis, colchicine, from the Baseline Visit until their Month 6 study visit as long as they are still on IP. Colchicine will be provided. In the US, colchicine 0.6 mg qd or twice daily (bid) is recommended for subjects with eCrCl >45 mL/min and qd to once every other day for subjects with eCrCl <45 mL/min ([Colcris \[US package insert\] Rev December 2016](#)). Based on medical history and the clinical judgement of the Investigator, decreasing the frequency to once every other day (or 3 times per week) is permitted. In the EU, colchicine 0.5 mg qd or bid is recommended. For patients with mild/moderate renal impairment (creatinine clearance 10 to 50 mL/min), the prescribing information recommends to reduce the dose or increase the interval between doses ([Colchicine 500 micrograms Tablets \[SmPC\] Rev October 2015](#)), such as decreasing to once every other day or every other day (3 times a week). Subjects who have a documented intolerance or allergy to colchicine or who are taking a concomitant medication contraindicated for use with colchicine (eg, P-gp or strong or moderate CYP3A4 inhibitors; see [Section 7.1.3](#)) are permitted to take low-dose oral corticosteroids (≤ 10 mg/day of prednisone, or prednisolone, or their equivalent) for a short course, such as through the Month 3 study visit, at the discretion of the Investigator. NSAIDs for gout flare prophylaxis will not be permitted due to the potential for nephrotoxicity.

Study site staff should refer to the local product labels for a description and complete prescribing information on XOI and gout flare prophylaxis.

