Commercially available gout flare prophylaxis, colchicine, will be provided through the Month 6 study visit. The dose will be 0.5 or 0.6 mg qd based on the local label. The frequency may be adjusted based on the local label, medical history of the subject, and clinical judgement (ie, taken every other day or 3 times a week if needed as appropriate, particularly for subjects with lower eCrCl). Subjects unable to take colchicine are permitted to take low-dose oral corticosteroids (ie, ≤ 10 mg/day of prednisone, or prednisolone, or their equivalent) for a short course, such as through the Month 3 study visit based on the Investigator's discretion.

Duration of Study and Treatment:

The overall duration of the study is anticipated to be approximately 5 years. The total duration of study participation for each subject (from Screening Visit 1 through the last study visit) is anticipated to be up to approximately 26 months.

Criteria for Evaluation:

Study Assessments:

Safety assessments will include an evaluation of AEs with particular focus on renal and CV events, clinical laboratory parameters (hematology, serum chemistry, urinalysis), and vital signs.

Efficacy assessments will be based on an evaluation of sUA levels. Additional efficacy assessments will explore gout flares, tophi resolution, and patient-reported outcomes (eg, EuroQol Five Dimensions Questionnaire 3 level, Sheehan Disability Score, and Work Productivity and Activity Impairment Questionnaire: Specific Health Problem).

Other assessments will include physical examinations and electrocardiograms (ECGs), as well as collecting medical history, Baseline gout characteristics, previous and concomitant therapies, and treatment compliance.

Safety Endpoints

- Absolute and percent change from Baseline in eCrCl to Month 24.

- Absolute and percent change from Baseline in eCrCl over the study period, including the last value on and off treatment.
- Incidence of serum creatinine (sCr) elevations ($\geq 1.5 \times$ Baseline) over the study period.
- Incidence of subjects meeting criteria (eg, based on sCr or eCrCl criteria) for treatment discontinuations over the study period.
- Incidence of renal-related and kidney stone treatment-emergent AEs (TEAEs) and serious AEs (SAEs).
- Prevalence of contributing factors to renal SAEs as adjudicated by the REAC.
- Incidence of CEAC-adjudicated Major Adverse Cardiovascular Event (MACE; CV death, nonfatal myocardial infarction, and nonfatal stroke).

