5.2.2. Gout Flare Prophylaxis

Gout flare prophylaxis, colchicine, will be provided through the Month 6 study visit. The dose of colchicine will be 0.5 or 0.6 mg qd based on the local label. The frequency may be adjusted based on the local label, medical history of the subject, and clinical judgement (ie, dosed every other day or 3 times a week if needed as appropriate, particularly for subjects with lower eCrCl).

Subjects unable to take colchicine (ie, those who have a documented intolerance or allergy to colchicine or who are taking a concomitant medication contraindicated for use with colchicine [eg, P-gp or strong/moderate CYP3A4 inhibitors, see [Section 7.1.3](#)]) are permitted to take low-dose oral corticosteroids (ie, ≤ 10 mg/day of prednisone, or prednisolone, or their equivalent) for a short course, such as through the Month 3 study visit, at the discretion of the Investigator. The steroid regimen should be individualized for each subject based on the need for gout flare

prophylaxis and potential side effects of persistent corticosteroid use, such as in relation to comorbid conditions.

If IP is permanently discontinued prior to the end of the gout flare prophylaxis period, the gout flare prophylaxis should be discontinued. If IP is interrupted and re-initiated, subjects can re-initiate gout flare prophylaxis at the discretion of the Investigator. Investigators should consider reinitiating gout flare prophylaxis based on the clinical circumstances.

The use of NSAIDs for gout flare prophylaxis is not permitted.

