5.3.2.2.1. Colchicine

Subjects are required to continue gout flare prophylaxis with colchicine through their Month 6 study visit unless they become intolerant or develop toxicity to the colchicine. Gout flare prophylaxis with colchicine may be interrupted or discontinued prior to the expected Month 6 study visit due to an AE or tolerability. If colchicine is interrupted for any reason in the gout flare prophylaxis period, it should be restarted when medically appropriate. Subjects should be encouraged to continue on colchicine as tolerated through the Month 6 study visit, but may decrease the dose or increase the interval between doses (ie, from once daily to once every other day).

If a subject requires treatment with cyclosporine, ranolazine, or strong/moderate CYP3A inhibitors (eg, clarithromycin, fluconazole, diltiazem; see [Section 7.1.3](#)) prior to their Month 6 study visit, then colchicine must be interrupted or discontinued.

Subjects who are unable to take colchicine during the gout flare prophylaxis period should, when medically appropriate, switch to a short course of low-dose oral corticosteroids. If switching is not medically appropriate, randomized subjects may continue in the study without gout flare prophylaxis.

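### Colchicine prophylaxis is once daily with reductions only in the Synopsis and Section 5.2.2, but once or twice daily in Section 5.3.1, and the passages need reconciling

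*Combined protocol and SAP*

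**What the plan says.** Five places in the protocol bear on how often colchicine is taken.

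- **Synopsis, Other Study Treatments:** "The dose will be 0.5 or 0.6 mg qd based on the local label".
- **Section 5.2.2:** "The dose of colchicine will be 0.5 or 0.6 mg qd based on the local label". Sites are allowed to adjust how often it is taken on the strength of the local label, the subject's history and clinical judgement. The adjustment is then spelled out as "ie, dosed every other day or 3 times a week if needed as appropriate, particularly for subjects with lower eCrCl".
- **Section 5.3.1:** "In the US, colchicine 0.6 mg qd or twice daily (bid) is recommended for subjects with eCrCl >45 mL/min". In the lower US band the section gives a different range, "qd to once every other day for subjects with eCrCl <45 mL/min". For Europe, "In the EU, colchicine 0.5 mg qd or bid is recommended". The next sentence, which opens "For patients with mild/moderate renal impairment (creatinine clearance 10 to 50 mL/min", reports that the prescribing information advises a lower dose or a longer interval in that range. The section cites the US and EU labels and ends by referring site staff to the local labels.
- **Section 5.3.2.2.1:** a subject may lower the dose or lengthen the interval, explained as "ie, from once daily to once every other day".
- **Section 8.3.1:** colchicine is listed among the study-supplied medications, all of which are to be taken in the morning. The reader is then sent to Section 5.3 for administration details.

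**The concern.** The Synopsis and Section 5.2.2 phrase the once-daily dose as what subjects will receive, and every adjustment they describe goes downward. Section 5.3.1 carries the title of the dosing instructions and adds a twice-daily option. A site that works from one section can reach a different permitted daily amount from a site that works from the other.

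Every enrolled subject has moderate renal impairment, and prophylaxis runs from Baseline to the Month 6 visit. The protocol itself lists gastrointestinal and, rarely, more severe events with low-dose colchicine (Section 1.2.3), and safety is the primary objective. An ambiguous instruction on daily amount is therefore first a matter of subject safety. It also has a practical side. Twice-daily use follows Section 5.3.1 but can be read as departing from Section 5.2.2, so it is unclear whether it would count as a protocol deviation. The Per-Protocol Population in Section 9.3 is defined by the absence of major deviations.

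**Working it through.** The protocol states no statistical figure on this point, so the check is a comparison of the text plus simple arithmetic.

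**1. The instructions side by side**

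| Place | Regimen | Direction of adjustment |
|---|---|---|
| Synopsis | 0.5 or 0.6 mg once daily | Less frequent only |
| 5.2.2 | 0.5 or 0.6 mg once daily | Less frequent only |
| 5.3.1, US, eCrCl above 45 | 0.6 mg once or twice daily | Decrease in frequency permitted |
| 5.3.1, US, eCrCl below 45 | Once daily to every other day | As above |
| 5.3.1, EU | 0.5 mg once or twice daily | Lower dose or longer interval at creatinine clearance 10 to 50 |
| 5.3.2.2.1 | Once daily as the starting point | Downward |
| 8.3.1 | Morning intake | Not addressed |

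**2. Does Section 5.2.2 already allow twice daily?** It ties frequency to the local label, which could be read as opening the door. But the list that explains the adjustment is introduced as a definition rather than as examples, and it holds only reductions. Nothing says that a labelled twice-daily regimen overrides the once-daily statement.

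**3. Which section would a site follow?** Section 3.1 points to Section 5.3 for more on prophylaxis dosing, and Section 8.3.1 points there for administration. The cross-references therefore lead to the section with the twice-daily option, and no rule of precedence is given. Section 8.3.1 also pulls the other way, since a twice-daily regimen does not fit morning-only intake.

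**4. Size of the difference.** Daily amount = tablet strength × doses per day.

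- US: 0.6 × 2 = 1.2 mg against 0.6 × 1 = 0.6 mg. Ratio 1.2 / 0.6 = 2.
- EU: 0.5 × 2 = 1.0 mg against 0.5 × 1 = 0.5 mg. Ratio 1.0 / 0.5 = 2.

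**5. Where in the eCrCl range it applies.** Enrolment requires an average Screening eCrCl of 30.0 to <60.0 mL/min (Section 4.2). The US option covers values above 45 and below 60. The EU option stands without a renal qualifier only above 50 and below 60, which is a narrower range.

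**6. How many subjects.** On Screening values, both ranges lie inside the 45.0 to <60.0 stratum, planned at about 50% of about 600: 0.5 × 600 = 300 across all regions (Sections 3.1 and 4.1). That is an upper limit. Twice daily is optional, some subjects will take corticosteroids instead, and the split between US and European sites is not given. The number could lie anywhere from none to about 300.

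**7. The value 45 exactly.** The US bands are above 45 and below 45, so 45 itself falls in neither. Section 5.4 places 45.0 in the upper randomization stratum. Because once daily appears in both US bands and in Section 5.2.2, a subject at 45 still has an instruction. This is a tidy-up only.

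**The case against.** The strongest reply is that Section 5.3.1 merely reports the labels. The US sentence cites the package insert and speaks of a recommendation. The European text cites its product information. The only permission on frequency that the section expressly gives the investigator is to decrease it. Read with Sections 5.2.2, 5.3.2.2.1 and 8.3.1, the protocol can be taken as one coherent plan: once daily, reductions allowed, label text for orientation. A site that chooses once daily above 45 mL/min complies with every passage.

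Much of this stands, and it softens the conflict. It does not remove it. The US sentence is written for the trial's subjects by eCrCl band, under a heading that announces dosing instructions, and it is not marked as background. Two careful sites could still reach different answers.

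A reader might also infer more than the text supports:

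- **That about half the subjects at US sites face a doubled amount.** The option is not a requirement, the roughly 300 in the upper stratum are counted across all regions, and the US share is not stated.
- **That the effect could be larger in the EU.** The ratio is the same twofold, and the advice for 10 to 50 mL/min leaves a narrower unqualified range than in the US.
- **That subjects at exactly 45 mL/min have no dose.** Once daily is common to both US bands.
- **That the treatment comparison is biased.** Colchicine is background therapy in both randomized, double-blind arms, and some variation by label and clinical judgement is intended. The documents show no mechanism for a difference between arms and allow no estimate of any effect on adverse events or flares.

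**Conclusion.** The inconsistency is real and worth correcting. Four places (the Synopsis and Sections 5.2.2, 5.3.2.2.1 and 8.3.1) fit once-daily dosing with downward adjustment. Section 5.3.1, the place to which sites are directed, also presents twice daily, for US subjects above 45 mL/min and in the EU subject to the advice for 10 to 50 mL/min. The permitted daily amount can therefore be read as differing by up to a factor of two in the upper part of the enrolled eCrCl range.

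The conclusion rests on reading the list of adjustments in Section 5.2.2 as complete and on the absence of any statement that the label text in Section 5.3.1 is background. If the sponsor intends that text as background, the remedy is to say so. The point concerns clarity of instruction and subject safety. It does not undermine the randomized comparison, and the number of subjects affected cannot be determined from the documents. No view is taken here on which regimen is appropriate.

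**What to change.** Reconcile the Synopsis and Sections 5.2.2, 5.3.1, 5.3.2.2.1 and 8.3.1 so that a single study instruction on colchicine frequency applies. State in Section 5.3.1 whether the label text is background or a permitted study regimen, and make the morning-intake statement in Section 8.3.1 consistent with the answer. As a minor tidy-up, word the US eCrCl bands so that exactly 45 mL/min is covered. The clinical team decides the content.

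The cost is protocol wording, which under Section 11.13 means a formal amendment, and a clarification to sites. It requires no change to the sample size or the statistical analyses.

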5.3.2. Dose Adjustments, Interruptions, and Discontinuations

IP, XOI, and gout flare prophylaxis should not be interrupted or discontinued if a subject experiences an acute gout flare.

5.3.2.1. Investigational Product and Xanthine Oxidase Inhibitors

IP (lesinurad or placebo) is only permitted at 200 mg qd. No dose reductions or dose escalations of IP are permitted. The prescribed dose and dosing regimen of XOI should also be continued unchanged throughout the study, unless adjusted for toxicity. Study treatment (IP or XOI) may be interrupted due to AEs or for suspected toxicity.

If XOI is interrupted for any reason, **IP must be interrupted concurrently**. When medically appropriate, the XOI should be resumed, at which time IP may also be resumed. The XOI may be resumed at the same dose; lower doses (if available) are only permitted if the XOI had been interrupted due to a TEAE considered related to that XOI. If resumed at a lower dose, the XOI should be increased up to the original dose, as tolerated. Subjects should not be maintained on a dose of allopurinol <200 mg daily.

If IP is interrupted for any reason, the subject is permitted to continue XOI, as tolerated. When medically appropriate, IP should be resumed, but must only be resumed if the subject is taking XOI.

5.3.2.1.1. Interruption or Discontinuation of Investigational Product Due to Changes in Kidney Function

Kidney function will be monitored throughout the study by measuring sCr and calculating eCrCl by Cockcroft-Gault formula using ideal body weight. All clinically meaningful changes in kidney function should be evaluated and managed as medically appropriate, including interrupting IP and study medications if needed.

IP must be **temporarily interrupted** if a subject experiences an absolute sCr ≥ 4.0 mg/dL or an eCrCl <20 mL/min (based on central laboratory results), and the subject will be required to return to the site for retesting (see [Section 6.12](#)). IP may be resumed at the Investigator's discretion if eCrCl is within 15% of Baseline if this occurs through the Month 12 study visit, or if eCrCl is within 20% of Baseline if this occurs from the Month 12 study visit through the Month 24 study visit.

IP should be **permanently discontinued** if there are more than 3 episodes of interruption of IP due to any of the following:

- If the Investigator or Healthcare Provider temporarily interrupts IP due to changes in kidney function,
- If the Investigator or Healthcare Provider temporarily interrupts IP due to any safety concerns due to IP, or
- Protocol-specified criteria for interruption are met (ie, sCR ≥ 4.0 mg/dL or eCrCl <20 mL/min).

An episode is defined as the interruption and then re-initiation of IP, regardless of the duration of the interruption. The fourth interruption should be considered permanent when based on the above criteria.

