4.2. Inclusion Criteria

Each subject must meet the following criteria to be enrolled in this study.

1. Subject is able to understand the study procedures, the risks involved, and willing to provide written informed consent before the first study related activity.
2. Subject is willing to adhere to the protocol schedule.
3. Subject is ≥ 18 years and ≤ 85 years of age.
4. Subject has a diagnosis of gout.
5. Subject has moderate renal impairment with estimated creatinine clearance (eCrCl calculated by the Cockcroft-Gault formula using ideal body weight) 25.0 to ≤ 65.0 mL/min at Screening Visits 1 and 2 and an average eCrCl for both screening visits of 30.0 to < 60.0 mL/min.
6. Subject has been taking an XOI as urate-lowering therapy (ULT) indicated for the treatment of gout for at least 4 weeks prior to Screening at a stable, medically appropriate dose, as determined by the Investigator. The minimum dose of allopurinol is 200 mg daily, and the minimum dose of febuxostat is the lowest approved dose per the local product label.
7. Subject has a serum uric acid level ≥ 6.0 mg/dL (357 $\mu\text{mol/L}$) at Screening Visits 1 and 2.
8. Subject is male or female; females must not be pregnant or breastfeeding and females of childbearing potential must agree to use non-hormonal contraception during the Screening Period and while taking IP.
9. Subject has a body mass index < 45 kg/m².

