6.12.1. Estimated Creatinine Clearance Decline From Baseline

Baseline Through the Month 12 Study Visit

From Baseline through the Month 12 study visit, if a subject experiences an eCrCl decline >30% from Baseline, the subject will return to the site within 1 to 2 weeks (Retest 1) for a retest.

- If any retest eCrCl declines \leq 15% from Baseline, no further retests are required and the subject may continue the protocol-scheduled visits.

- If the Week 1 to 2 retest (Retest 1) eCrCl declines >15% from Baseline, the subject will return to the site for a retest approximately 3 to 4 weeks (Retest 2) after the initial eCrCl decline was noted.
- If the Week 3 to 4 retest (Retest 2) eCrCl declines >15% from Baseline, the subject will return to the site for a retest approximately 7 to 8 weeks (Retest 3) after the initial eCrCl decline was noted.
- Thereafter, additional retests may be done at the Investigators discretion or the subject may continue the protocol-scheduled visits. If subject's eCrCl does not return to $\leq 15\%$ of Baseline, IP can be continued and additional retesting is not required; medical treatment and evaluation should be sought as appropriate.

If a subject has persistent decline in their renal function (ie, stable at an eCrCl level 15% to 30% below Baseline) or has permanently discontinued IP, retesting may be at the Investigator's discretion based on medical appropriateness.

Month 12 Study Visit to Month 24 Study Visit

From the Month 12 study visit to the Month 24 study visit, if a subject experiences an eCrCl decline >40% from Baseline, the subject will return to the site within 1 to 2 weeks for a retest (Retest 1).

- Retests 2 (Weeks 3 to 4) and 3 (Weeks 7 to 8) should be performed unless eCrCl declines $\leq 20\%$ from Baseline.
- If any retest eCrCl declines $\leq 20\%$ from Baseline, no further retests are required and the subject may continue the protocol-scheduled visits.
- If a subject has persistent decline in their renal function (ie, stable at an eCrCl level 20% to 40% below Baseline) or has permanently discontinued IP, retesting may be at the Investigator's discretion based on medical appropriateness.

Investigators are encouraged to keep subjects on IP during the Retest periods as clinically appropriate and providing sCr is <4.0 mg/dL and eCrCl ≥ 20.0 mL/min.

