6.12.2. Absolute Serum Creatinine ≥ 4.0 mg/dL or Estimated Creatinine Clearance <20 mL/min

If a subject experiences an absolute sCr ≥ 4.0 mg/dL or an eCrCl <20 mL/min at any time during the study, IP must be **temporarily interrupted**, and the subject will return to the site within 1 to 2 weeks (Retest 1) for a retest.

Baseline Through the Month 12 Study Visit

- From Baseline through the Month 12 study visit, if any retest eCrCl declines $\leq 15\%$ from Baseline and sCr <4.0 mg/dL and an eCrCl ≥ 20 mL/min, no further retests are required and the subject may restart IP, at the Investigator's discretion, and continue the protocol-scheduled visits. The re-initiation of IP may occur regardless of the duration of the interruption.

- If Retest 1 eCrCl declines >15% from Baseline or sCr \geq 4.0 mg/dL or an eCrCl <20 mL/min, the subject will return to the site for a retest approximately 3 to 4 weeks (Retest 2) after the initial decline was noted.
- If Retest 2 eCrCl declines >15% from Baseline or sCr \geq 4.0 mg/dL or an eCrCl <20 mL/min, the subject will return to the site for a retest approximately 7 to 8 weeks (Retest 3) after the initial decline was noted.
- After Retest 3, subjects should continue the protocol-scheduled visits. If eCrCl is \leq 15% of the Baseline and sCr <4.0 mg/dL and eCrCl \geq 20 mL/min, the subject may restart IP, at the Investigator's discretion.

Month 12 Study Visit to Month 24 Study Visit

- From the Month 12 study visit to the Month 24 study visit, Retests 2 (Weeks 3 to 4) and 3 (Weeks 7 to 8) should be performed if eCrCl declines >20% from Baseline or sCr \geq 4.0 mg/dL or eCrCl <20 mL/min.
- If any retest eCrCl declines \leq 20% from Baseline and sCr <4.0 mg/dL and an eCrCl \geq 20 mL/min, no further retests are required and the subject may restart IP, at the Investigator's discretion, and continue the protocol-scheduled visits. The re-initiation of IP may occur regardless of the duration of the interruption.

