9.1. General Considerations

All subjects will be randomized to either lesinurad 200 mg or matching placebo in combination with an XOI in a 1:1 ratio and stratified by the following stratification factors:

- Screening eCrCl: the average eCrCl of Screening Visit 1 and Screening Visit 2 (30.0 to <45.0 mL/min or 45.0 to <60.0 mL/min).
- Baseline measurable target tophus status: present or absent.
- Type of XOI: allopurinol or febuxostat.

This study will enroll approximately 50% of subjects with eCrCl 30.0 to <45.0 mL/min and approximately 50% with eCrCl 45.0 to <60.0 mL/min. There is no planned sample size requirement on the number of subjects enrolled by type of XOI or Baseline tophus status. However, a stratification variable (eg, Baseline measurable target tophus status [present/absent]) may be dropped from the stratified analysis (eg, mixed model repeated measures [MMRM] or Cochran Mantel Haenszel [CMH]) if the number of subjects in any stratum is very low (eg, <10% of total subjects). The decision to drop a stratification variable will be made prior to database lock and will be documented in the SAP.

All safety and efficacy data will be listed and summarized by treatment group.

Baseline is defined as the last observed measurement prior to the first dose of IP, unless otherwise specified.

Descriptive statistics will consist of the number of subjects (n), mean, standard deviation (SD), median, minimum, and maximum for continuous variables, and counts and percentages for categorical variables.

Unless otherwise specified, all confidence intervals (CIs) will be calculated at the 95% level and all hypothesis tests will be performed at the 0.05 level. All analyses including summaries and listings will be performed using SAS[®] software version 9.1 or higher.

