APPENDIX C. RETESTING SCHEMA FOR SUBJECTS WITH CHANGES IN KIDNEY FUNCTION

Abbreviations: BL, Baseline; eCrCl, estimated creatinine clearance; IP, investigational product; sCr, serum creatinine.

RETEST 1, RETEST 2, and RETEST 3 are performed approximately 1 to 2 weeks, 2 to 4 weeks, and 7 to 8 weeks relative to the test result that first met the criteria.

^a If the criteria for IP interruption have been met on 3 separate episodes during the course of the study, IP needs to be permanently discontinued.

^b For all assessments after the Month 12 study visit, the criterion for retesting changes to “eCrCl >40% decline from BL”.

^c For all assessments after the Month 12 study visit, the criterion for resolution changes to “eCrCl ≤20% decline from BL”.

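### The condition for restarting IP after a mandatory renal stop differs between Sections 5.3.2.1.1 and 6.12.2, and one restart threshold cannot be met as written

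*Combined protocol and SAP*

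**What the plan says.** Section 5.3.2.1.1 requires IP to be interrupted at sCr ≥4.0 mg/dL or "an eCrCl <20 mL/min (based on central laboratory results), and the subject will be required to return to the site for retesting". The next sentence leaves resumption to the Investigator's "discretion if eCrCl is within 15% of Baseline if this occurs through the Month 12 study visit", and allows 20% from Month 12 to Month 24. That sentence contains no sCr limit and no absolute eCrCl limit. The pointer to Section 6.12 is attached to the retesting, not to the resumption.

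Section 6.12.2 deals with the same interruption. Through Month 12, if any retest shows an eCrCl decline of ≤15% together with sCr <4.0 mg/dL and eCrCl ≥20 mL/min, "no further retests are required and the subject may restart IP". The Month 12 to 24 part has the same three conditions with 20% in place of 15%. A further bullet, for the time after Retest 3 and only in the part through Month 12, allows restart if eCrCl is ≤15% "of the Baseline and sCr <4.0 mg/dL and eCrCl" is at least 20 mL/min.

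Section 6.12.1 uses the same form of words: if eCrCl does not return to ≤15% "of Baseline, IP can be continued and additional retesting is not required". Note c of Appendix C has the correct form: "For all assessments after the Month 12 study visit, the criterion for resolution changes to" a decline of ≤20%.

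**The concern.** This rule decides when a subject who has just met the trial's mandatory renal stopping limit may be exposed to IP again. Renal safety is the focus of the primary objective, and up to about 300 sites would apply the rule. A site that looks only at the dosing section finds a looser condition than a site that looks at the retesting section. Taken alone, the dosing sentence can allow restart at a laboratory value for which the sentence before it requires a stop. The bullet for the time after Retest 3 has the opposite fault: taken literally, it allows restart for nobody.

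**Working it through.** The plan gives no figure for this rule, so there is none to reproduce. The check compares the two texts and then asks which subjects could fall between them.

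**Inputs.** Stop and restart limits: Sections 5.3.2.1.1 and 6.12.2. Formulas: Section 6.9.1. For men, eCrCl = (140 − age) × IBW / (72 × sCr) and IBW = 50 + 2.3 × (height in inches − 60); for women, IBW starts from 45.5 and the result is multiplied by 0.85. Entry range: 25.0 to 65.0 mL/min at each Screening visit and "an average eCrCl for both screening visits of 30.0 to < 60.0 mL/min" (Section 4.2). Section 9.1: "Baseline is defined as the last observed measurement prior to the first dose of IP". Baseline eCrCl is thus a separate measurement with no entry limit of its own.

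**1. Logic.** Section 6.12.2 needs (decline within the limit) and (sCr <4.0) and (eCrCl ≥20). Section 5.3.2.1.1 needs only the first. Whoever meets 6.12.2 meets 5.3.2.1.1, but not the reverse.

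**2. Route through the sCr limit.** With age unchanged, sCr 4.0 lies within a 15% decline if Baseline sCr ≥ 4.0 × 0.85 = 3.4 mg/dL, and within 20% if ≥ 4.0 × 0.80 = 3.2 mg/dL.

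Example: man of 40, 72 in, Baseline eCrCl 30.
- IBW = 50 + 2.3 × 12 = 77.6 kg; Baseline sCr = 100 × 77.6 / (72 × 30) = 3.59 mg/dL.
- At sCr 4.0: eCrCl = 7760 / 288 = 26.94, a decline of 10.2%. Section 5.3.2.1.1 permits restart and 6.12.2 refuses.
- A 15% decline is reached at 3.593 / 0.85 = 4.227 mg/dL (one year older: 99 × 77.6 / (72 × 25.5) = 4.184). The sections therefore differ for retest sCr from 4.0 to about 4.2.
- Under the 20% rule the upper end is 4.446 one year older, or 4.408 at 1.84 years (24 × 28 = 672 days).

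Counter-example: man of 60, 70 in, Baseline eCrCl 30. Baseline sCr is 80 × 73.0 / 2160 = 2.70. At sCr 4.0 his eCrCl is 20.28, a decline of 32.4%, so both sections refuse.

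The highest age at the retest for which the sections can differ is 140 − 3.4 × 72 × B / IBW for Baseline eCrCl B, with 3.2 in place of 3.4 for the 20% rule. For men, in whole years:

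| Height (IBW, kg) | B = 30: 15% / 20% rule | B = 27: 15% / 20% rule |
|---|---|---|
| 68 in (68.4) | 32 / 38 | 43 / 49 |
| 70 in (73.0) | 39 / 45 | 49 / 54 |
| 72 in (77.6) | 45 / 50 | 54 / 59 |
| 74 in (82.2) | 50 / 55 | 59 / 64 |

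At B = 45 and 74 in the limits are 6.0 and 13.9 years, below the minimum age of 18, so no man up to 74 in is affected. For women with B = 30 the limits are 13.9 and 21.3 years at 70 in, and 28.8 and 35.3 years at 74 in. At 66 in no woman is affected.

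**3. Route through the eCrCl limit.** 0.85 × B < 20 only if B < 23.5, and 0.80 × B < 20 only if B < 25.0. At B = 23.0, a retest of 19.7 is a decline of 1 − 19.7/23.0 = 14.3%, which 5.3.2.1.1 permits and 6.12.2 refuses. Such a Baseline would have to lie at least 1 − 23.53/30 = 21.6% (15% rule) or 1 − 25/30 = 16.7% (20% rule) below a Screening average of 30. This route adds very little.

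**4. The bullet for the time after Retest 3, read literally.** At 65.0 mL/min, the highest value allowed at a Screening visit, 15% is 9.75 mL/min. Reaching 20 mL/min needs B ≥ 20 / 0.15 = 133.3. Read as a decline of ≤15%, the restart level is 25.5 mL/min at B = 30 and 51 mL/min at B = 60; both can be reached and agree with the limit of 20.

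**The case against.** The strongest reply is that this is copy-editing. Read as a whole, the paragraph in 5.3.2.1.1 makes the stop mandatory and the restart optional. A retest at sCr 4.1 mg/dL would still meet the stop limit, so a discretionary restart could not sensibly override it. The full rule stands in 6.12.2, and a site can comply with both sections by following the stricter one. The misworded bullet has only one sensible meaning, because the neighbouring bullets and Appendix C speak of a decline from Baseline. The bullet for any retest already covers Retest 3 correctly, so the faulty one matters only for later measurements. The slip in 6.12.1 changes no action, since the literal condition leads to what was intended anyway. The Appendix C diagram is not visible and may state the full rule.

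All of this lowers the weight of the point, but it does not remove it. The restart sentence does omit two conditions that the other section imposes, real combinations of age, height and Baseline eCrCl reach the gap, and an operative threshold is wrong as printed. That a careful reader would work out the intent is a reason to rate it minor.

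**Conclusion.** The point holds, at minor weight. The sCr condition is the one that can change a decision; the missing eCrCl floor is nearly redundant. The worked cases rest on the protocol's own formulas and on chosen ages, heights and Baseline values. The documents give no distribution of these, so no count of subjects is possible beyond saying that it would be small. No gap is claimed for Months 12 to 24 as such: both sections and note c of Appendix C apply the 20% limit there. Only the notes to Appendix C could be checked. Type I error, power, sample size and the analysis models are untouched.

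**What to change.** Make these changes in the next amendment:

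- Section 5.3.2.1.1: *After a mandatory renal stop, restart of IP is at the Investigator's discretion and requires all three of: eCrCl decline from Baseline ≤15% (≤20% after the Month 12 visit); sCr <4.0 mg/dL; eCrCl ≥20 mL/min. See Section 6.12.2.*
- Section 6.12.2, bullet for the time after Retest 3: state the threshold as *an eCrCl decline of ≤15% from Baseline*.
- Section 6.12.1, matching sentence: *if the decline in eCrCl from Baseline remains >15%*.
- Section 6.12, note on the interruption criterion: point to 6.12.2 instead of 6.12.1 (editorial).

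The cost is three short wording edits and one cross-reference.
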